## D. Research Design & Methods

### D.1 Aims

**D.1.a Primary Aim:** Evaluate the efficacy of a diabetes focused inpatient discharge order set (DOS) on reducing HbA1c at 24 weeks compared to enhanced standard care (ESC) among hospitalized basal insulin requiring patients with uncontrolled diabetes.

**D.1.b. Secondary Aims:**

- Evaluate the efficacy of a diabetes focused inpatient discharge order set (DOS) on reducing HbA1c at 12-24 weeks compared to enhanced standard care (ESC) among hospitalized basal insulin requiring patients with uncontrolled diabetes.
- Determine whether the DOS in conjunction with nurse supported self-titration of basal insulin glargine U300 is associated with improved persistence with insulin therapy, adequate dose titration, and use of self-monitored blood glucose.
- Determine whether the DOS is associated with improved discharge instructions and processes of care for insulin-requiring patients. This will be measured in terms of clarity of instructions, adequacy and completeness of prescriptions for insulin and diabetes supplies, and follow-up plan.

### D.2. Research Design

**D.2.a Study Design:** In this 24 week randomized controlled trial, hospitalized insulin-requiring patients with type 2 diabetes and poor glycemic control (HbA1c >8.5%) will receive standard of care insulin therapy including basal insulin glargine U300 (TOUJEO®) plus additional background therapy (non-insulin and prandial insulin therapies) with either a diabetes focused discharge order set (DOS) and follow-up communication to facilitate insulin titration and outpatient follow-up or enhanced standard care (ESC).

**D.2.b Study Population:** 222 patients (type 2 diabetes) will be recruited. Inclusion/exclusion criteria appear in Table 6. Hospitalized patients with type 2 diabetes (HbA1c >8.5%) who are receiving basal insulin at least 10 unit per day and are able to provide informed consent will be approached.

Patients must have access to some form of communication (phone, electronic patient messaging) post discharge and be willing to obtain HbA1c at follow-up. Patients will be identified through daily screening of the inpatient medical and surgical services throughout the institution.

**Table 6: Inclusion and Exclusion Criteria**

Inclusion Criteria	Exclusion Criteria
Diagnosis of diabetes, type 2 ≥3 months duration HbA1c >8.5% Ages 25-75 years Phone or electronic media availability Receiving basal insulin >10 unit/day	Sensitive admissions: Prisoners Pregnancy Unable to consent or follow study directions in English Expected nursing facility stay longer than 2 weeks

### D.2.c. Recruitment

Participants will be identified from the diabetes consult, medicine and surgery ward services at the main OSU Hospital System and OSU East hospital. OSU East is a community hospital with a high percentage of indigent and minority patients. An efficient system is already in place for screening patients for inpatient diabetes studies. Each morning, the research assistant screens services through the electronic medical record, initially

filtering by insulin use and then HbA1c. Permission will be obtained from the attending physician of the admitting inpatient service to contact the patient. Current annual inpatient diabetes physician and educator consults at OSU main and OSU East are roughly 3000 per year, but there are approximately 13,000 admissions with a diagnosis code for diabetes each year. Approximately 1000 admissions per year have an HbA1c >9%. Diabetes nurse practitioners and certified diabetes educators are available weekdays at both sites.

#### **D.2.d. Enrollment and Randomization**

Enrollment is expected at a rate of approximately 3 patients per week with the last patient enrolled within 18 months to allow completion and analysis of all data within 3 years. The study and all study-related documents will be approved by the OSU IRB. Written informed consent will be obtained. Patients will be stratified by pre-admission insulin therapy (yes/no) and randomized using a random number generator program.

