**Secondary:**

- Change in HbA1c from baseline to 12 weeks (+/-2 weeks) post-discharge
- Change in fasting plasma glucose (FPG) from baseline in DOS vs ESC
- % of patients achieving HbA1C 7% in DOS vs ESC
- % of patients achieving HbA1C 6.5% in DOS vs ESC
- % of patients achieving individualized HbA1c target in DOS vs. ESC: HEDIS HbA1c target (<8% if age  $\geq$  65 years or known history of ischemic vascular disease, heart failure, advanced kidney disease [eGFR <30], dementia, proliferative retinopathy/blindness, advanced neuropathy [history of ulcer or amputation] or history of severe hypoglycemia; otherwise goal is <7%)
- Proportion of patients with accurate and complete discharge orders for insulin and related supplies.
- Adherence to glargine U300 (>80% of doses) at 2, and 24 weeks
- Proportion of patients who remain on glargine U300 at 24 weeks
- Mean dose of glargine U300 at 2 and 24 weeks
- Proportion of patients who follow up with their primary care provider within 2, 6 weeks of discharge
- Incidence of documented symptomatic (BG <54 mg/dl) hypoglycemia

**Analysis:** Outcomes will be further analyzed by type of diabetes, pre-admission therapy, and bolus insulin requirements.

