### H.2.a. Statistical Power and Sample Size

The sample size for our study was based on a comparison of change in HbA1c over three months adjusting for baseline covariates related to change in HbA1c: age, whether or not patient is new to insulin, and dose of insulin; the first two were selected based on our preliminary data and the latter was selected based on an expected relationship. The following expression, adapted from Oakes and Feldman, was used to calculate the number of individuals per group:

$$n/group = \frac{4\sigma^2(1-\rho)(1-R^2)(Z_{1-\alpha/2} + Z_{1-\beta})^2}{\Delta^2}$$

where  $\sigma$  is the standard deviation of HbA1c,  $\rho$  is the correlation between baseline and 24 week HbA1c levels,  $R^2$  is the proportion of variability in change in HbA1c explained by the baseline covariates,  $\Delta$  is the difference in change in HbA1c between treatment groups, and  $Z_{1-\alpha/2}$  and  $Z_{1-\beta}$  are standard normal quantiles calculated at the two-sided type-I error rate ( $\alpha$ ) and power (1- $\beta$ ). Using parameter values based on our preliminary data ( $\sigma = 2.2\%$ ,  $\rho = 0.25$ ,  $R^2 = 0.5$ ) and based on the effect observed by Wexler ( $\Delta = 0.8\%$ ), we will need 89 individuals per treatment group with 24 week follow-up to achieve 80% power at  $\alpha = 0.05$ . Since we expect 20% attrition, we will recruit 111 individuals per group into our study. The study is powered to detect a difference in the primary endpoint only. However, additional secondary endpoints of strong interest are pre-specified and included in the analysis.

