**H.2.c Primary Aim: To determine whether a Discharge order set with nursing support (DOS) is associated with lower HbA1c at 24 weeks post-program than enhanced standard care (ESC) alone.** We will test for a difference in 24 week change in HbA1c between the DOS and ESC groups using a linear mixed model for the longitudinal HbA1c measurements. Our model will contain a random subject-specific effect and fixed effects of time (baseline vs. 24 weeks), treatment, a treatment-by-time interaction, and baseline covariates related to change, which we expect to include age, whether or not patient is new to insulin, and dose of insulin based on our preliminary data. We will adjust for changes in prandial insulin dose by including dose as a time-varying covariate in our mixed models. The inclusion of covariates is not to account for differences in these factors across treatment groups (which we don't expect due to randomization) but to increase the precision of our treatment effect estimate. A Wald test of the treatment-by-time interaction will be used to test our primary hypothesis that DOS affects 24 weeks change in Hb1Ac.

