Based upon preliminary data, we found that approximately 30% were of African American race. We are enrolling a wide age range, 25-75, in order to achieve optimal external validity, but have excluded the younger and older participants due to insufficient numbers in those ranges and possibly different educational needs, that may involve people (family) other than the patient. Participants are anticipated to be sick and have other comorbidities (in our pilot data, 70% were admitted for a problem that was not directly related to diabetes). However, all participants will be free-living in the community and have a phone. Due to bias introduced by additional support staff at institutions such as nursing homes and rehabilitation centers, these participants will be excluded. Participants who are unable to provide consent in English will be excluded as this number is very small and will hinder motivational interviewing (MI) process. Other vulnerable populations, such as prisoners will be excluded. Pregnant individuals will be excluded since the HbA1c is not as reliable and because such individuals have different motivations and follow-up already in place.

Permission will be obtained from the attending physician of the admitting inpatient service prior to approaching participants for enrollment. Randomization will be conducted using a computerized random number generator program that is weighted and will be stratified by race. The frequency of telephone follow-up is felt to be adequate to establish reasonable endpoints for reinforcement of behavior and capture a realistic window for readmission.

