#### **A.4. Importance of the Knowledge to be Gained**

The importance of the knowledge is in the understanding of the role of diabetes, in particular diabetes education and PN, on the discharge process. Currently, diabetes is overlooked in the hospital and at discharge, despite its importance for the overall well-being of the patient. The current protocol provides an easily adaptable hierarchical process for inpatient to outpatient transitions in care for a population of complicated medical patients. Currently, few randomized studies have examined whether telephonic follow-up or post-discharge support is effective in this population. The rising epidemic of diabetes will continue to contribute significantly to the morbidity of these patients, frequently necessitating hospital care. Providing solutions to this problem is of considerable urgency. Therefore, the potential benefits outweigh the given the aforementioned risks.

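### The plan names two different randomisation stratifiers, and the primary model as written does not adjust its tested treatment-by-time term for either of them or for the other baseline covariates

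*Combined protocol and SAP*

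**What the plan says.** **Stratification.** D.2.d (Enrollment and Randomization): "Patients will be stratified by pre-admission insulin therapy (yes/no) and randomized using a random number generator program". Human Subjects A.1.a: "Randomization will be conducted using a computerized random number generator program that is weighted and will be stratified by race". Weighting is not defined anywhere, and no block scheme is described.

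**Allocation and size.** H.2.a derives 89 evaluable patients per group and, for 20% attrition, states that "we will recruit 111 individuals per group into our study". D.2.b and Human Subjects A.1.a give the total as 222.

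**Primary model.** H.2.c specifies a random subject effect with "fixed effects of time (baseline vs. 24 weeks), treatment, a treatment-by-time interaction, and baseline covariates related to change". The covariates expected are age, new-to-insulin status and insulin dose. Prandial insulin dose is added as a time-varying covariate. The hypothesis is tested by a Wald test of treatment-by-time, and the covariates are there "to increase the precision of our treatment effect estimate".

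**Subgroups.** The synopsis says: "Outcomes will be further analyzed by type of diabetes, pre-admission therapy, and bolus insulin requirements". Race is neither a subgroup factor there nor a covariate in H.2.a or H.2.c.

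**The concern.** Two separate matters meet here.

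First, the randomisation list cannot be built from the text. A list made from D.2.d ignores race, and one made from Human Subjects A.1.a ignores pre-admission insulin. If both factors were intended, neither section says so. The analysis strata are equally undetermined.

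Second, whichever factor is used, H.2.c does not adjust the tested quantity for it. The test concerns the difference in change. A covariate that enters only as a main effect shifts a patient's baseline and 24-week values equally, so it drops out of the change. That applies to every listed baseline covariate, and H.2.a gives those covariates credit for half the variance of change. What is at stake is therefore most of the precision assumed in the sample size, and to a lesser degree the calibration of the test after stratification.

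**Working it through.** **1. The plan's own figure.** Inputs from H.2.a: SD 2.2, correlation 0.25, R² 0.5, difference 0.8, two-sided 5%, 80% power.

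n = 4 × 2.2² × 0.75 × 0.5 × (1.960 + 0.842)² / 0.8² = 89.04 per group, and 89 / 0.8 = 111.25. The stated 89 and 111 reproduce under equal allocation.

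**2. What the model as written delivers.** With both time points observed and no time-varying covariate, the treatment-by-time estimate is the difference in mean change between arms. A time-constant main effect cancels. In 1,500 simulated trials per setting, adding one moved the estimate by no more than 2e-15. R² for the tested term is then 0.

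- Variance of change: 2 × 2.2² × 0.75 = 7.26.
- SE at 89 per group with R² = 0: √(2 × 7.26 / 89) = 0.404. Power = Φ(0.8/0.404 − 1.96) = 50.8%.
- SE with R² = 0.5: √(2 × 3.63 / 89) = 0.286. Power = 80.0%.
- Evaluable patients needed for 80% at R² = 0: 178.07 per group, twice the stated 89.04.

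Simulating the random-intercept model gave:

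| Setting | Main effects only | Covariate-by-time |
|---|---|---|
| 89 per arm, complete data | 51–52% | 80–81% |
| 111 per arm, 20% of 24-week values missing | 52–55% | 81% |

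With the missing values, individual estimates moved by up to 0.05 or 0.21 HbA1c points, depending on how the covariate was assumed to act. The empirical SE stayed at 0.38–0.39, against 0.27–0.28 with covariate-by-time. With a time-varying dose term (40 illustrative data sets, assumed dose patterns), a stratifier main effect moved the estimate by 0.06 on average, with an SE ratio of 0.999. The cancellation is then no longer exact, but precision still does not improve.

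**3. The insulin stratifier alone.** The pilot's univariable table gives 0.95 for any insulin on admission. The type 2 row in that table is −1.39, half of the group gap 0.018 − (−2.76) = 2.778. That points to effect coding, so the yes/no difference would be 2 × 0.95 = 1.90. Read without that coding, it is 0.95.

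The row also pools diabetes types, whereas the trial enrols type 2 only. Assume 10 of the 41 pilot patients with change data had type 1 (24%, close to 19/77 in the full sample), with insulin shares of 18/19 and 26/58. Type 1 patients are then 40.5% of insulin users and 3.0% of non-users. Diabetes type alone produces (0.405 − 0.030) × 2.778 = 1.04 of the 1.90, leaving about 0.86.

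With share p = 26/58 = 0.448, R² = d² × p(1 − p) / 7.26:

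| Difference d | R² | SE with stratifier-by-time | Reduction from 0.404 |
|---|---|---|---|
| 1.90 | 12.3% | 0.378 | 6% |
| 0.95 | 3.1% | 0.398 | 1.5% |
| 0.86 | 2.5% | 0.399 | 1.3% |

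Race: a coefficient of 0.32 (or 0.64 if effect coded) with a 33% share gives R² of 0.3% to 1.2%, an SE reduction below 1%.

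**4. Type I error if stratifier-by-time is left out.** Simulated with 178 patients in all, no treatment effect, complete data and no other covariates:

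| Allocation within strata | d = 1.90 | d = 0.90 |
|---|---|---|
| Balanced | 3.5–4.0% | 4.9% |
| Simple randomisation | 5.0–5.3% | 5.2% |

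The ranges at 1.90 come from separate runs. The mechanism is visible at 1.90: under balance the mean model SE is 0.404 against an empirical SD of 0.38; under simple randomisation the two agree at about 0.40.

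**The case against.** **The two factors are compatible.** Neither section says only, so both could be used. That is fair, but no sentence says they are, and each section reads as the full description.

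**The race sentence may be text carried over from another protocol.** Human Subjects A.1.a justifies the language exclusion because "this number is very small and will hinder motivational interviewing (MI) process", and A.4 refers to knowledge about "in particular diabetes education and PN, on the discharge process". Neither element belongs to the intervention in section F. A reader might infer that D.2.d simply prevails, and the covariates and subgroup plan fit D.2.d better. This remains an inference about the text's origin; the documents do not settle it.

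**New-to-insulin status is already in the model.** It is, and it would be wrong to say that the stratifier is absent. The point is that a main effect does not adjust the tested interaction.

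**Covariates related to change may mean covariate-by-time terms.** This is the strongest reply, and H.2.a's definition of R² on change supports it as the intention. But H.2.c names the treatment-by-time interaction explicitly and names no other. The text is under-specified, and one line would settle it.

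**Time-varying prandial dose might do the work.** It is a post-randomisation variable and is neither stratifier.

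**Conclusion.** The conflict over the stratifier is certain from the text. The modelling gap holds for H.2.c as written. It is exact with two complete time points and no time-varying term, and very nearly so otherwise. Its main cost is the R² = 0.5 that the sample size assumes: about 51% power instead of 80% at 89 per group if the covariates stay as main effects. The stratifier's own share is modest: about 1% to 6% of the SE for insulin, depending on a small, univariable pilot estimate that mixes diabetes types, and negligible for race.

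Three stronger readings are not supported:

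- *The primary test is conservative.* That requires balance within strata, and no blocking is described. Even with balance, the effect is clear only if the insulin difference is near 1.9. Nothing here inflates type I error.
- *The sample size is wrong, or is safe.* The arithmetic is right under 1:1. Whether it delivers 80% depends on covariate-by-time terms being fitted and on R² = 0.5 being achieved.
- *Weighted means unequal allocation.* Every figure given for the arms is equal, so 1:1 is not contradicted; the word is merely undefined.

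**What to change.** 1. Name the same stratifier or stratifiers in D.2.d and Human Subjects A.1.a.
2. In Human Subjects A.1.a, replace the reference to weighting with the 1:1 allocation that 111 per group implies, or define it.
3. In H.2.c, enter each stratifier actually used, and the other listed baseline covariates (age, new-to-insulin status, baseline insulin dose), each with its interaction with time. Adding only the stratifier interaction would leave most of the assumed precision unrealised.

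The cost is a wording correction in two sections and a few extra model terms. No new data are needed: race, diabetes history and concomitant medications are already collected at baseline (D.2.e and Table 9).

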#### **D.2.e. Initial Assessment:** Trained interviewers will perform initial data collection.

- Contact information, including email address, best times to reach the patient, contact information for 2 additional individuals, and PCP.
- Type of diabetes, duration, complications, reason for hospital admission
- Age, gender, race and ethnicity, education level, marital status, work status, home ownership, insurance coverage, medical history, concomitant medications, weight, height, BMI, standard of care lab results
- Social support is an environmental factor that is associated with readmissions, determines behavior in SCT and influences self-efficacy. It will be measured using the Multidimensional Scale of Perceived Social Support (PSSS).
- Health literacy is a determinant of hospital readmissions and will be assessed using the Newest Vital Sign.
- Diabetes Empowerment Scale Short-Form (DES-SF) measures perceived self-efficacy and predicts adherence to a therapeutic plan. The DES-SF has been shown to have acceptable reliability ( $\alpha=0.84$ ).
- Comorbidity is key determinant of readmission; it is measured with the Charlson comorbidity index.
- It is anticipated that nearly all patients who are hospitalized with an HbA1c >8.5% will go home on insulin therapy. The complexity of the discharge regimen will be assessed as number of injections per day, total units per day, and number of glucose checks per day.

#### **D.2.f. Retention**

Staffing will be funded by the study to reach patients after hours. Incentives will be provided for completing the follow-up HbA1c at the 12 and 24 week visits. Patients will be contacted at pre-arranged times, with up to 3 attempts during the week of the encounter. In the event of failure to contact, a letter/email will be sent and staff will then reach out to the patient designated secondary contacts. The medical records will be monitored at OSU and queries to the patient's designated primary care physician will be made up to 24 weeks following enrollment.

#### **D.2.g. Program Completion**

Participants will receive an order to complete the HbA1c at 12 and 24 weeks at any OSU lab. A reminder letter will be sent 1 week prior to the date and a phone call reminder will occur 2 days before the visit. Study team will complete the 12 week and 24 week call and search the electronic medical record and primary provider's chart for HbA1c and healthcare utilization at 12 and 24 weeks.

**E. Study Drug:** Patients in both groups will be provided standard of care insulin therapy throughout the study, including insulin glargine (TOUJEO® U300) plus additional background therapy (non-insulin and prandial insulin therapies), based upon discharge team preference. The starting dose will be determined during hospitalization from the dose of glargine/detemir U100 in a 1:1 dose conversion. Upon discharge, standard titration instructions (every 4 days) will be implemented in the DOS group but will be left to the discretion of the discharge team in the ESC group.

**Table 7. Intervention procedures**

	Enhanced Standard Care	Discharge Order Set
Diabetes Education	Basic survival skills	Basic survival skills
Discharge orders	Per primary team: medication reconciliation, prescriptions and instructions, follow-up appointments	Discharge order set in addition to primary team
Patient Care Resource Manager	Yes	Yes
U300 glargine at discharge	Yes	Yes
U300 glargine titration	Per primary team	Yes
Follow-up	Coordinator call to assess adherence, outcomes	Nurse call to confirm titration

## **F. Intervention**

### **F.1 Enhanced Standard Care**

#### **F.1.a. Discharge**

In the enhanced standard care arm, the discharge regimen will be determined by the primary team with input from the diabetes service if requested. All patients will receive standard discharge instructions using the electronic medical record as per usual practice. Hospital discharge is coordinated by the primary team and existing patient care resource manager who arranges follow-up prior to discharge. A discharge summary is sent to the primary provider per routine practice. Patients are instructed to maintain a glucose and insulin diary. Patients will receive survival skills education by a dedicated nurse.

